8.6.2 Serious adverse events

An SAE is defined as any adverse event [appearance of (or worsening of any pre-existing)] undesirable sign(s), symptom(s), or medical conditions(s) which meets any one of the following criteria:

- fatal
- life-threatening

Life-threatening in the context of a SAE refers to a reaction in which the participant was at risk of death at the time of the reaction; it does not refer to a reaction that hypothetically might have

caused death if it were more severe (please refer to the International Council for Harmonization ICH-E2D Guidelines).

- results in persistent or significant disability/incapacity.
- constitutes a congenital anomaly/birth defect, fetal death or a congenital abnormality or birth defect.
- requires inpatient hospitalization or prolongation of existing hospitalization, unless hospitalization is for:
 - routine treatment or monitoring of the studied indication, not associated with any deterioration in condition.
 - elective or pre-planned treatment for a pre-existing condition that is unrelated to the indication under study (and has not worsened since signing the informed consent).
 - social reasons and respite care in the absence of any deterioration in the participant's general condition.
 - treatment on an emergency outpatient basis for an event not fulfilling any of the definitions of a SAE given above and not resulting in hospital admission.
- is medically significant, e.g. defined as an event that jeopardizes the participant or may require medical or surgical intervention to prevent one of the outcomes listed above.

Medical and scientific judgment should be exercised in deciding whether other situations should be considered serious reactions, such as important medical events that might not be immediately life-threatening or result in death or hospitalization but might jeopardize the participant or might require intervention to prevent one of the other outcomes listed above. Such events should be considered as "medically significant." Examples of such events are intensive treatment in an emergency room or at home for allergic bronchospasm, blood dyscrasias, or convulsions that do not result in hospitalization or development of dependency or abuse (please refer to the [ICH E2D 2004](#)).

All new malignant neoplasms will be assessed as serious under "medically significant" if other seriousness criteria are not met.

All reports of intentional misuse and abuse of the product are also considered serious adverse events irrespective of whether a clinical event has occurred.

Any suspected transmission via a medicinal product of an infectious agent is also considered a serious adverse reaction.

8.6.3 SAE reporting

To ensure participant safety, every SAE, regardless of causality, occurring after the participant has provided informed consent and until last study visit must be reported to Novartis safety immediately, without undue delay, but under no circumstances later than within 24 hours of obtaining knowledge of the events (Note: If more stringent, local regulations regarding reporting timelines prevail). Novartis detailed instructions regarding the submission process and requirements are to be found in the investigator folder provided to each site. Information about all SAEs is collected and recorded on the Electronic Serious Adverse Event (eSAE) or Serious Adverse Event Report Form; all applicable sections of the form must be completed in order to provide a clinically thorough report. SAEs occurring after the participant has provided

informed consent until the time the participant is deemed a Screen Failure must be reported to Novartis.

Event common in the participant population under study: Investigators will report AEs or SAEs that are commonly seen in the study population but they will not be unblinded and will not be reported as suspected unexpected serious adverse reaction (SUSAR) to regulatory agencies, ECs, or investigators during the study. In clinical trials evaluating treatments for high morbidity and/or high mortality disease states, SAEs that are known consequences of the underlying disease or condition under investigation, or events common in the study population, are anticipated to occur with some frequency during the course of the study, regardless of drug exposure. While the investigator must still report all SAEs, SUSARS considered consistent with the following SAE Preferred Terms will not be unblinded and reported in an expedited timeframe to regulatory agencies, ECs or investigators during the course of the study. These events will be presented in the clinical study report at the end of the study:

Sepsis, Septic shock, Acute kidney injury, Multiple organ dysfunction syndrome, Acute respiratory distress syndrome, Disseminated intravascular coagulation, Pneumonia, Hypotension, Fever, Tachypnea, Leucocytosis, Leucopenia, Respiratory alkalosis, Metabolic acidosis.

If specifically requested by a local Health Authority (HA), pre-specified SAEs that also meet the criteria for SUSARs will be expedited to this HA as blinded reports. INs will not be issued for these events.

OR

Pre-specified SAEs commonly observed in the study population that occur in patients under the jurisdiction of the requesting Health Authority will be expedited to the Health Authority as unblinded reports; INs will be issued for these events.

All follow-up information for the SAE including information on complications, progression of the initial SAE and recurrent episodes must be reported as follow-up to the original episode immediately, without undue delay, but under no circumstances later than within 24 hours of the investigator receiving the follow-up information (Note: If more stringent, local regulations regarding reporting timelines prevail). An SAE occurring at a different time interval or otherwise considered completely unrelated to a previously reported one must be reported separately as a new event.

If the SAE is not previously documented in the Investigator's Brochure or Package Insert (new occurrence) and is thought to be related to the study treatment, a CMO & PS Department associate may urgently require further information from the investigator for health authority reporting. Novartis may need to issue an Investigator Notification (IN) to inform all investigators involved in any study with the same study treatment that this SAE has been reported.

SUSARs will be collected and reported to the competent authorities and relevant ethics committees in accordance with *European (EU) Guidance 2011/C 172/01* or as per national regulatory requirements in participating countries.

Any SAEs experienced after the last study visit should only be reported to Novartis Safety if the investigator suspects a causal relationship to study treatment, unless otherwise specified by local law/regulations.

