6.2.3 Instruction for prescribing and taking study treatment

There should be a period of at least 1 hour after the infusion whereby the participant requires close observation. Patient care should be managed as per local medical practice.

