Injection of a foreign protein into humans may trigger immune response with or without inflammatory signs and symptoms. Such reactions, if they occur, may be immediate or delayed up to several weeks. Since TIN816 is a modified version of a naturally occurring human protein, immunogenicity may occur.

The CTIN816B12201 study will apply single dosing. A prolonged IV infusion time of 2 hours will reduce C_{max} exposure, and a single dose administration of TIN816 will further reduce the exposure duration. Despite the very low risk of a theoretical infusion reaction due to Monocyte chemoattractant protein-1 (MCP-1) related histamine release, signs and symptoms of any allergic reaction should be closely monitored, and IV infusion could be stopped at any time.

Anti-drug antibody mediated reactions (immunogenicity)

As with other therapeutic recombinant proteins, there is a possibility of TIN inducing an immune response in human participants. Presence of host cell proteins in preclinical and clinical TIN816 batches, is also known to enhance the risk of immunogenicity ([Vanderlaan et al., 2018](#)). The primary consequence of immunogenicity may be altered PK and

PD properties of the drug, leading to a potential loss in efficacy. There is also a theoretical possibility of immune-mediated reactions.

Development of anti-TIN816 antibodies and their neutralization potential of TIN816 and/or endogenous CD39 will be assessed in dedicated plate and cell-based in-vitro assays and are interpreted in the context of PK, PD and safety. Potential reactions related to such antibodies, such as antibody-mediated arthropathy, should be monitored closely.

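### The exemption from expedited reporting in Protocol 8.6.3 covers suspected reactions, has no exception for infusion timing or events of special interest, and conflicts with other text in the same section

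*Protocol*

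**What the plan says.** Protocol 8.6.3 requires sites to report every SAE to the sponsor within 24 hours, whatever its cause. It then sets apart events common in this population, which "will not be reported as suspected unexpected serious adverse reaction (SUSAR) to regulatory agencies, ECs, or investigators during the study". The operative sentence is explicit that suspected reactions are included: "SUSARS considered consistent with the following SAE Preferred Terms will not be unblinded and reported in an expedited timeframe". The list has 14 terms and ends "Disseminated intravascular coagulation, Pneumonia, Hypotension, Fever, Tachypnea, Leucocytosis, Leucopenia, Respiratory alkalosis, Metabolic acidosis". Exempt events are to appear in the clinical study report.

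Three further statements in 8.6.3 bear on the same events:

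- If a local health authority asks, listed events that are also SUSARs are expedited to it as blinded reports, and "INs will not be issued for these events".
- After a bare OR, listed events in patients under the requesting authority's jurisdiction "will be expedited to the Health Authority as unblinded reports; INs will be issued for these events".
- A later paragraph says "SUSARs will be collected and reported to the competent authorities and relevant ethics committees", following EU guidance or national rules. It does not mention the exemption.

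Infusion reactions and hypersensitivity are events of special interest in 8.6.6, which says "signs and symptoms of any allergic reaction should be closely monitored, and IV infusion could be stopped at any time". Section 6.2.3 adds: "There should be a period of at least 1 hour after the infusion whereby the participant requires close observation".

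**The concern.** The reason given for the exemption is that these events are expected in sepsis whether or not the drug is given. That justifies not expediting events of the disease. It does not justify holding back an event that has been judged a suspected drug reaction. As drafted, what matters is whether the event is considered consistent with a listed term. When it began relative to the infusion, and whether it is of special interest, do not enter the rule.

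At stake is whether ethics committees, authorities and other sites hear of a suspected reaction while further patients are being dosed. The human exposure described in Protocol 2.2 is 24 healthy volunteers on TIN816, and 2.3.2.3 reports no infusion reaction among them, so the documents describe no experience in septic patients. The protocol summary states that there is no data monitoring committee. Safety against placebo is the secondary objective.

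**Working it through.** No arithmetic in the plan bears on this point, so the check sets the passages side by side.

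**Step 1. Which events does the exemption affect?** A SUSAR must be suspected, unexpected and serious. A listed event judged not suspected is not a SUSAR, so the SUSAR exemption makes no difference to it. Protocol 8.6.1 already tells investigators that progression of the underlying illness will usually be assessed as not suspected. The listed events that the exemption changes are therefore those where a drug cause was thought plausible despite that guidance.

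**Step 2. Is there overlap with a named drug risk?** Protocol 8.6.6 allows that a reaction to the protein may come with inflammatory signs, mentions a theoretical histamine-related infusion reaction, and says reactions may be immediate or delayed by up to several weeks. Protocol 8.4.2 collects temperature and blood pressure immediately before and after the infusion, and 8.4 includes respiratory rate among the safety vital signs. Fever, hypotension and tachypnea are abnormalities of these measures, and all three are on the list. The documents do not say that an infusion reaction presents this way, so the link is inferred.

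**Step 3. Does the outcome depend on how the event is recorded?**

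| Serious, unexpected event recorded as | Judged suspected? | On the list? | Default under 8.6.3 |
|---|---|---|---|
| Infusion reaction, hypersensitivity or bleeding | Yes | No | Reportable as a SUSAR |
| Hypotension, fever or tachypnea, no diagnosis made | Yes | Yes | Not unblinded, not expedited |
| Hypotension, fever or tachypnea | No | Yes | Not a SUSAR; exemption makes no difference |

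The gap is the second row.

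**Step 4. Do the procedures in 8.6.3 agree with one another?**

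| Text | Blinding of the report | Investigator notification |
|---|---|---|
| Default exemption | No unblinding, no expedited report | None during the study |
| Authority request, before OR | Blinded | Not issued |
| Authority request, after OR | Unblinded | Issued |
| General SUSAR sentence | Not stated | Not stated; reports go to authorities and ethics committees |

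The second and third rows are opposites, and the text does not choose between them. The fourth contradicts the first, because it carries no exception and no cross-reference.

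**Step 5. How many people are exposed?** With 20 participants randomized 3:1, 20 × 3/4 = 15 receive TIN816. The documents give no expected rate of serious suspected events of this kind, so the number affected cannot be estimated.

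**The case against.** The strongest reply is that the protocol already limits the problem. Section 8.6.1 asks for a diagnosis, where possible, in place of separate signs, so a recognised infusion reaction would be recorded as one and would fall outside the list. The exemption turns on events being considered consistent with a term, which leaves room for medical judgement. An exemption for expected events also has a stated rationale in a high-mortality population. All of this stands, and it narrows the gap to suspected events recorded only as a sign. It does not close it: the diagnosis rule applies only where a diagnosis is possible, and in a septic patient under blinded care the label may be uncertain.

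Three stronger readings are tempting and are not supported.

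- A reader might infer that suspected reactions matching the list can never be expedited. An authority can request reports, and 8.6.3 says the sponsor may need to issue an investigator notification for a new, related SAE. Section 10.1.2 provides for new safety information to be communicated as appropriate. These routes are discretionary or depend on a request, so the exemption is a default and not an absolute bar.
- A reader might infer that safety signals go unseen. Every SAE reaches the sponsor within 24 hours, Protocol 6.3.2 makes the sponsor's trial team unblinded, 2.3.2 mentions periodic safety review, and 7.5 allows termination for safety.
- A reader might infer from disseminated intravascular coagulation on the list that the drug's haemostatic risk is exempt. The named risk in 2.3.2.1 and 8.6.6 is bleeding through reduced platelet aggregation, and no bleeding term is listed. Section 2.3.2.1 also reports no change in PT, INR or APTT in healthy volunteers. Nothing in the documents ties TIN816 to that syndrome.

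**Conclusion.** The point holds in a limited form. By default, 8.6.3 withholds unblinding and expedited reporting for SUSARs consistent with 14 terms and makes no exception for infusion timing or special-interest status. The practical gap is onward notice to authorities, ethics committees and other sites of a suspected hypotension, fever or tachypnea event recorded without a diagnosis. This rests on one assumption from outside the documents: that an infusion or hypersensitivity reaction can appear as those signs.

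The internal contradiction needs no such assumption. The two OR procedures oppose each other, and the general SUSAR sentence is not reconciled with the exemption. The primary pharmacokinetic analysis is not affected. The change is worth making because it improves safety notice in a small trial with no data monitoring committee, at little cost.

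**What to change.** Amend Protocol 8.6.3 in three places.

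1. State that the exemption does not apply to a suspected event that starts during the infusion or the observation period of 6.2.3, or that is reported as an event of special interest under 8.6.6. The first limb covers at least 2 + 1 = 3 hours from the start of a 2-hour infusion. The second is needed because 8.6.6 allows for reactions delayed by several weeks; it takes effect when an event carries a sign-level term but is also flagged as special interest.
2. Keep only one of the two procedures joined by OR, as the sponsor and the authorities determine.
3. Reconcile the general SUSAR sentence with the exemption by cross-reference, so that the section states one rule.

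The cost is protocol wording, a few more expedited reports, and a few single-case unblindings among 20 participants. The primary endpoint is serum concentration, summarized descriptively, so those unblindings should matter little to it. No treatment or patient-management rule changes.

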7.1 Discontinuation of study treatment

Since this is a one time single dose intravenous infusion, a permanent interruption of the infusion will be considered as discontinuation from study treatment.

Discontinuation of study treatment for a participant occurs when study treatment is permanently stopped for any reason (prior to the planned completion of study treatment administration, if any) and can be initiated by either the participant or the Investigator.

The Investigator must discontinue study treatment for a given participant if, he/she believes that continuation would negatively impact the participant's well-being.

Discontinuation from study treatment is required under the following circumstances:

- Participant/guardian decision
- Any situation in which continued study participation might result in a safety risk to the participant

If discontinuation from study treatment occurs, the Investigator should make a reasonable effort to understand the primary reason for the participant's discontinuation from study treatment and record this information.

Participants who discontinue from study treatment agree to return for the end of treatment and follow-up visits indicated in [Section 1.3](#) Schedule of Activities.

If the participant cannot or is unwilling to attend any visit(s), the site staff should maintain regular telephone contact with the participant, or with a person pre-designated by the participant. This telephone contact should preferably be done according to the study visit schedule.

The Investigator must also contact the IRT to register the participant's discontinuation from study treatment.

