7.2 Participant discontinuation from the study

Discontinuation from study is defined as when a participant permanently stops any further protocol-required assessments or follow-up, for any reason.

If the participant agrees, a final evaluation at the time of the participant's study discontinuation should be made as detailed in [Section 1.3](#) Schedule of Activities.

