8.4 Safety and tolerability assessments

Safety assessments are specified below with [Section 1.3](#) Schedule of Activities detailing when each assessment is to be performed.

The following assessments will be considered safety measurements:

- Vital signs, including blood pressure, respiratory rate and body temperature at baseline Day 1 and at all post-baseline visits.
- Physical examination at screening, baseline Day 1, Day 14 and Day 90 visits.
- Local ECG at baseline Day 1 visit.

- Local arterial/venous blood gas sampling for PaO₂/carbon dioxide partial pressure (PaCO₂)/pH/HCO₃
- Local laboratory at screening, baseline Day 1 visit and at post-baseline visits.
 - Hematology at screening and baseline Day 1, Day 5, Day 14, Day 30 and Day 90 visits.
 - Clinical chemistry, including liver function parameters at screening and baseline Day 1, Day 5, Day 14, Day 30 and Day 90 visits.
 - Urinalysis at screening, baseline Day 1, Day 3, Day 5, Day 14, Day 30 and Day 90.
 - Coagulation parameters at screening, baseline Day 1, Day 5, Day 14, Day 30 and Day 90.
- Central laboratory for anti-drug antibodies at baseline (Day 1/ pre-dose) and at visits on Days 14, 30 and 90.
- Concomitant medication at screening and all visits from Day 1 to Day 90.
- AEs/SAEs during the duration of the study.
- Mortality (monitored continuously throughout the study)

For details on AE collection and reporting, refer to [Section 8.6](#).

As per [Section 4.5](#), during a public health emergency as declared by local or regional authorities i.e. pandemic, epidemic or natural disaster, that limits or prevents on-site study visits, regular phone or virtual calls can occur (every 4 weeks or more frequently if needed) for safety monitoring and discussion of the participant's health status until it is safe for the participant to visit the site again.

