8.6.1 Adverse events

An adverse event is any untoward medical occurrence (e.g. any unfavorable and unintended sign [including abnormal laboratory findings], symptom or disease) in a clinical investigation participant after providing written informed consent for participation in the study. Therefore, an AE may or may not be temporally or causally associated with the use of a medicinal (investigational) product.

The investigator has the responsibility for managing the safety of individual participant and identifying adverse events.

Novartis qualified medical personnel will be readily available to advise on study-related medical questions or problems.

The occurrence of adverse events must be sought by non-directive questioning of the participant at each visit during the study. Adverse events also may be detected when they are volunteered by the participant during or between visits or through physical examination findings, laboratory test findings, or other assessments.

Adverse events must be recorded under the signs, symptoms, or diagnosis associated with them, accompanied by the following information (as far as possible) (if the event is serious refer to [Section 8.6.2](#)):

1. The common terminology criteria for adverse events (CTCAE) grade (version 5 or higher). If CTCAE grading does not exist for an adverse event, use 1=mild; 2=moderate, 3=severe; and 4=life threatening. CTCAE grade 5 (death) is not used, but is collected in other eCRF (e.g., Study Completion, Death/Survival).
2. Its relationship to the study treatment. If the event is due to lack of efficacy or progression of underlying illness (i.e. progression of the study indication) the assessment of causality will usually be 'Not suspected.' The rationale for this guidance is that the symptoms of a lack of efficacy or progression of underlying illness are not caused by the trial drug, they happen in spite of its administration and/or both lack of efficacy and progression of underlying disease can only be evaluated meaningfully by an analysis of cohorts, not on a single participant .
3. Its duration (start and end dates or ongoing) and the outcome must be reported.

4. Whether it constitutes a SAE (see [Section 8.6.2](#) for definition of SAE) and which seriousness criteria have been met.

5. Action taken regarding with study treatment.

All adverse events must be treated appropriately. Treatment may include one or more of the following:

- Dose not changed

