- Drug interrupted/permanently discontinued

6. Its outcome.

Conditions that were already present at the time of informed consent should be recorded in medical history of the participant.

Adverse events (including lab abnormalities that constitute AEs) should be described using a diagnosis whenever possible, rather than individual underlying signs and symptoms.

Adverse event monitoring should be continued until last study visit.

Once an adverse event is detected, it must be followed until its resolution or until it is judged to be not recovered/not resolved (e.g. continuing at the end of the study), and assessment must be made at each visit (or more frequently, if necessary) of any changes in severity, the suspected relationship to the interventions required to treat it, and the outcome.

Information about adverse drug reactions for the investigational drug can be found in the Investigator's Brochure.

Abnormal laboratory values or test results constitute adverse events only if they fulfill at least one of the following criteria:

- they induce clinical signs or symptoms
- they are considered clinically significant
- they require therapy

Clinically significant abnormal laboratory values or test results must be identified through a review of values outside of normal ranges/clinically notable ranges, significant changes from baseline or the previous visit, or values which are considered to be non-typical in participant with the underlying disease. Alert ranges for laboratory and other test abnormalities are included in [Section 10.3](#).

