2.6.1 Secondary endpoints/secondary estimands

For all safety analyses, the safety set will be used. All summaries where appropriate (e.g. change from baseline summaries), listings and tables will be presented by treatment group.

Adverse events

All information obtained on adverse events will be displayed by treatment group and participant.

The number (and percentage) of participants with treatment emergent adverse events (events started after the first dose of study medication or events present prior to start of participant and investigator-blind treatment but increased in severity based on preferred term) will be summarized in the following ways:

- by treatment, primary system organ class and preferred term.
- by treatment, primary system organ class, preferred term and maximum severity.

Separate summaries will be provided for study medication related adverse events, death, serious adverse events, other significant adverse events leading to discontinuation.

The number (and proportion) of participants with following adverse events of special interest/related to potential risks will be summarized by treatment:

- bleeding
- perivascular/vascular mineralization
- infusion reaction and hypersensitivity
- anti-drug antibody mediated reactions (immunogenicity).

A participant with multiple adverse events within a primary system organ class is only counted once towards the total of the primary system organ class.

The following adverse events will be counted during 90-day study period:

- These events are those with an onset after the start of the treatment period, or which were present prior to the start of the treatment period but increased in severity, changed from being not suspected to being suspected of study treatment relationship, or developed into SAEs after the start of the treatment period.

Vital signs

Summary statistics will be provided for all vital signs data by treatment and visit/time. Where ranges are available, abnormalities (and relevant orthostatic changes) will be listed by treatment group, participant, and visit/time. If appropriate, summary statistics of the occurrence of abnormalities may be provided by treatment.

Graph of mean arterial pressure (MAP) over time will be provided by treatment. Of note MAP is defined as diastolic blood pressure + 1/3*pulse pressure, where pulse pressure =systolic blood pressure – diastolic blood pressure).

Clinical laboratory evaluations

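### No Day 90 vital status is required after a participant discontinues from the study, and the 'last study visit' that closes AE and SAE capture is undefined, so a later unrelated death may be missed

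*Protocol*

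**What the plan says.** **Capture window.** Protocol 8.6.1: "Adverse event monitoring should be continued until last study visit". Protocol 8.6.3 applies the same end point to SAEs of any causality, those "occurring after the participant has provided informed consent and until last study visit must be reported to Novartis safety immediately". For later events, "Any SAEs experienced after the last study visit should only be reported to Novartis Safety if the investigator suspects a causal relationship", with an exception where local law requires more. 'Last study visit' is not defined.

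**Causality guidance.** Protocol 8.6.1 covers events caused by the disease itself: "If the event is due to lack of efficacy or progression of underlying illness", causality will usually be rated as not suspected.

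**Leaving the study.** Protocol 7.2: "Discontinuation from study is defined as when a participant permanently stops any further protocol-required assessments or follow-up, for any reason". A final evaluation follows if the participant agrees. The definitions in 10.2.2 separate this from withdrawal of consent: a participant who discontinues from the study has not asked for use of data to stop.

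**Other routes.** For a participant whose infusion was permanently stopped and who will not attend visits, Protocol 7.1 says "the site staff should maintain regular telephone contact with the participant". Protocol 7.4 requires documented contact attempts for anyone who goes silent.

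**Analysis.** SAP 2.6.1: "The following adverse events will be counted during 90-day study period". Its main death summary is of treatment-emergent AEs with a fatal outcome. A wider summary of on-treatment and post-treatment deaths is to be given if appropriate, and all deaths in the clinical database are listed. The Safety set (Protocol 9.1, SAP 2.2) holds everyone dosed.

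**The concern.** Safety against placebo is the only listed secondary objective, and death is its least ambiguous component. The analysis assumes a 90-day window and keeps every dosed participant in the denominator. The collection rules do not clearly secure the matching numerator for someone who leaves early.

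Take a participant who completes the infusion, leaves on Day 20 after a final evaluation, and dies of sepsis on Day 40. If the exit evaluation counts as the last study visit, the death is reportable to the sponsor's safety group only if the investigator suspects the drug, and the guidance points the other way. No readable instruction tells the site to find out whether this person is alive at Day 90. A participant with unknown status could then be displayed as one without a fatal event. In arms this small, a single such case changes the picture.

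**Working it through.** **Step 1. Which participants are exposed to the gap?**

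| Participant | Governing text | Death before Day 90 captured? |
|---|---|---|
| Completes all visits | Schedule of activities: last visit is Day 90/EOS | Yes |
| Infusion stopped, stays in study | Protocol 7.1: visits or telephone contact | Yes, in principle |
| Stops attending without saying so | Protocol 7.4: documented contact attempts before being called lost | Sought, though no vital-status check is specified |
| Withdraws consent | Protocol 7.3: later data are missing | No, for legitimate reasons |
| Actively discontinues from study, consent not withdrawn | Protocol 7.2: final evaluation if agreed, nothing after | No stated route |

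The gap is essentially the last row.

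**Step 2. Can 'last study visit' fall before Day 90?** The text allows it. The schedule section (Protocol 1.3) has discontinuers do the final-visit assessments as soon as possible. SAP 2.1.1 treats completion as the Day 90 visit, or EOS for those who discontinue. The pregnancy section (Protocol 8.6.4) names the 90-day visit outright, so the authors fixed a day where they wanted one. Against this, Protocol 4.1 says all participants are followed for 90 days. Both readings are open, and sites could apply different ones.

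**Step 3. Denominators.** Inputs: about 20 randomized and 3:1 allocation (Protocol 4.1).
- TIN816: 20 × 3/4 = 15, which reproduces the arm size in Protocol 9.9.1.
- Placebo: 20 − 15 = 5.

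**Step 4. Effect of one missed death**, assuming all 20 are dosed:
- TIN816: 1/15 = 6.7 percentage points.
- Placebo: 1/5 = 20 percentage points.

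Illustration with invented counts:
- True: 4/15 = 26.7% against 2/5 = 40.0%, difference −13.3 points.
- One placebo death missed: 4/15 = 26.7% against 1/5 = 20.0%, difference +6.7 points.

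The direction reverses. The exact 95% intervals for placebo are very wide either way: 5% to 85% for 2/5, and 0.5% to 72% for 1/5.

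**Step 5. How likely is it?** The documents give no leaving rate, so both inputs are assumptions: e, the share leaving alive before Day 90, and q, the chance that a leaver dies between exit and Day 90. Expected missed deaths are 20·e·q. The chance of at least one is 1 − (1 − e·q)^20, if every such death goes unrecorded.

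| e | q | Expected missed | Chance of at least one |
|---|---|---|---|
| 5% | 10% | 0.1 | 1 − 0.995^20 = 9.5% |
| 10% | 20% | 0.4 | 1 − 0.98^20 = 33% |
| 20% | 40% | 1.6 | 1 − 0.92^20 = 81% |

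The range is wide because the inputs are unknown. The table shows that the event is not negligible; it does not predict it. The mortality of up to 65% cited in Protocol 2.2 is an upper figure for the condition, not the risk after surviving to exit, so it is not used for q.

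**The case against.** **The relatedness rule is not a database rule.** A reader might infer that causality opinion filters which deaths are analysed. The sentence in 8.6.3 governs reports to the sponsor's safety group. Protocol 8.6.1 says death is collected on other eCRF pages, and the SAP lists every death in the database. This stands, and rules out that inference. It does not close the gap: neither text says how a site learns of a death after a 7.2 exit, and a listing cannot show a death that was never entered.

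**The early-exit reading is only one reading.** This also stands. The defect is an undefined term, not an established rule that capture stops at exit.

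**Other text reduces the problem.** Section 7.4 covers those who merely stop attending, and Protocol 1.3 says missed visits should not lead to automatic discontinuation. Follow-up of an SAE already reported must itself be reported, so some later deaths could enter that way. These narrow the gap to active discontinuation.

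**No contradiction is shown.** A reader might see a conflict with Protocol 8.4, which lists mortality as monitored continuously during the study, or with the SAP's 90-day count. Neither promises data on people who have left. They are better described as lacking a supporting procedure.

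**Redaction.** Parts of the schedule and some protocol and SAP sections cannot be read. A vital-status procedure there cannot be excluded, but the readable sections on discontinuation and safety reporting contain none.

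**Conclusion.** The point holds in a limited form. For a participant who actively discontinues from the study before Day 90 without withdrawing consent, the readable text requires no vital status, and a later death judged unrelated may go unrecorded while the participant stays in the Safety set. One such death changes crude mortality by 6.7 points on TIN816 or 20 points on placebo, given arms of 15 and 5 with everyone dosed.

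A reader might go further and conclude that mortality is biased downward, or that the trial cannot report Day 90 mortality for everyone dosed. The documents do not support either as a flat statement: both require that someone leaves, and the bias also requires an unobserved death. The analysis is descriptive, so no test or error rate is affected, and a comparison against five placebo participants is imprecise in any case. This is a cheap improvement to the plan, not a flaw that undermines it.

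**What to change.** 1. **Protocol 8.6.1 and 8.6.3:** define 'last study visit' relative to the scheduled Day 90 visit, and state what applies to a participant who discontinues from the study before then.
2. **Protocol 7.2:** for every dosed participant who discontinues from the study, require Day 90 vital status and any date of death, by telephone or medical-record check, unless consent is withdrawn, the participant objects or local law forbids it. Record it on the existing death/survival eCRF whatever the causality.
3. **SAP 2.6.1, Deaths:** report Day 90 status as alive, dead or unknown, by arm, for the whole Safety set.

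Full AE collection should not be extended to people who have stopped all follow-up. AEs are sought by questioning at visits, so this would be impractical.

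**Cost:** one call or record check per leaver, a protocol amendment, and possibly consent wording to permit the check. No added participants and no added clinical procedures.
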